A comparative study of preoperative and intraoperative carbon nanoparticles injection in patients undergoing thyroid cancer surgery

Research program

NCT ID: Not yet assigned

Date of document: 2025.01.11

Research program

I. Background of the study

1. Thyroid Cancer and Thyroid Surgery

Thyroid cancer is a common malignant tumor in the neck, and its incidence accounts for about 1% of the total incidence of malignant tumors, and its incidence rate ranks fifth in the incidence of tumors. In recent years, with the improvement of residents' health awareness and the wide implementation of neck examination, the detection rate of thyroid cancer has been increasing rapidly, and the patient group is found to have a tendency to be younger, while female patients are predominant and significantly higher than male patients.

Except for undifferentiated cancer, surgery is still one of the most important treatments for all types of thyroid cancer, which is supplemented by radionuclide, TSH inhibition, and external radiation, etc. Surgery can effectively improve the prognosis of the disease by completely removing the lesions. Surgical treatment of the thyroid gland is mainly divided into two parts: thyroidectomy and cervical lymph node dissection. The extent of thyroidectomy is still divided, but there is a consensus that the lobes should be the minimum extent of resection. In recent years, total resection and subtotal resection have also been gradually accepted.

There is a basic consensus that the minimum scope of lymph node dissection is central lymph node (VI) dissection, because the main metastatic route of thyroid cancer is lymphatic metastasis, and it may appear earlier, for example, the lymphatic metastasis rate of initially treated patients with papillary thyroid cancer can be as high as 20% to 90%. For patients with positive lymph nodes or highly suspected in auxiliary examination, modified radical translymph node dissection is needed, i.e., on the basis of thyroidectomy, translymph node dissection in zone II-VI is performed while preserving sternocleidomastoid muscle, internal jugular vein and parasympathetic nerves. It is currently believed that under the premise of surgical safety, the number of central lymph node dissection can effectively reduce the risk of postoperative recurrence, and at the same time can be combined with the pathology to provide patients with precise treatment and clarify the stage of cancer.

In the past, open neck surgery was used in clinical practice, which would leave scarring on the neck and affect the appearance, and at the same time, patients could lose part of the function of the anterior cervical skin, and a few patients had a foreign body sensation and skin linkage during swallowing activities, which had an impact on the patients' satisfaction with the surgery. Thus, in recent years, with the development of minimally invasive medical technology, the luminal thyroid surgery has come into people's view. Currently, the more commonly performed laparoscopic surgeries can be categorized into axillary approach, oral vestibular approach, thoracic breast approach, etc., and there are also case reports of multi-approach combined surgeries. These new laparoscopic surgical treatments have been widely used in the clinic. While meeting the requirements of tumor resection as much as possible, laparoscopic surgery is gradually accepted by patients because of its smaller incision and stronger protection of the function and integrity of the neck skin.

2. Postoperative complications of thyroid cancer

Hypoparathyroidism and laryngeal recurrent nerve injury are the most common complications of radical thyroid cancer surgery, whether it is open surgery or luminal approach, and once these complications occur, they will have a serious impact on the patient's quality of life in the postoperative period.

(1). Hypoparathyroidism

A domestic study on the occurrence of hypoparathyroidism after radical thyroid cancer surgery in patients with differentiated thyroid cancer showed that the incidence of hypoparathyroidism after radical thyroid cancer surgery ranged from 0.5% to 65.0%. In clinical practice, hypoparathyroidism is usually categorized as temporary and permanent. Temporary hypoparathyroidism is mainly characterized by transient hypocalcemic symptoms such as numbness of hands and feet; permanent hypoparathyroidism is characterized by long-term hypocalcemic symptoms such as numbness of hands and feet and twitching of limbs, and in severe cases, it may also lead to convulsions and laryngeal spasms, which can seriously affect the patient's health and even cause death. Transient hypoparathyroidism with transient hypocalcemia is usually considered to be caused by destruction of the parathyroid blood supply (the blood supply of parathyroid glands mainly comes from the thyroid

artery, and ligation of the thyroid blood supply artery during bilateral thyroidectomy during surgery can have an effect on the blood supply to the parathyroid glands, which can become dysfunctional due to obstruction of venous return and stagnation of the parathyroid glands); whereas, permanent hypoparathyroidism is mostly related to the destruction of the blood supply to the parathyroid glands. Permanent hypoparathyroidism is mostly associated with disruption of the parathyroid blood supply leading to ischemic necrosis or misdirected parathyroidectomy.

Previous studies have suggested that the incidence of postoperative temporary hypoparathyroidism ranges from 7% to 38%, with most patients returning to normal within 6 months as serum parathyroid hormone levels rise. In contrast, the incidence of permanent hypoparathyroidism ranges from 1% to 7% of patients who do not have complete resolution of symptoms at 6 months after surgery and who also require oral calcium to maintain normal calcium levels. There is no doubt that hypothyroidism can have a serious impact on the quality of life and health of patients and greatly reduces their satisfaction with surgery.

(2). Injury to the recurrent laryngeal nerve

Injury to the recurrent laryngeal nerve usually occurs during dissection of the thyroid artery, ligation, or freeing of the trachea after severing the thyroid isthmus. Patients with unilateral recurrent laryngeal nerve injury will suffer from hoarseness, mild respiratory and swallowing difficulties, and choking on drinking water; patients with bilateral recurrent laryngeal nerve injury will suffer from respiratory difficulties, respiratory failure, and even asphyxia in severe cases. At this stage, it is usually advocated to expose the laryngeal recurrent nerve in the process of freeing the trachea, which can reduce the incidence of laryngeal recurrent nerve injury to a certain extent.

3. carbon nanoparticles and carbon nanoparticles negative contrast technology

Carbon nanoparticles is an effective and harmless negative developer, and there have been many studies confirming that carbon nanoparticles can be used to identify parathyroid glands in thyroid surgery. Nanocarbon suspensions consist of nanocarbon particles with an average diameter of 150 nm. The cellular gap between capillary

endothelial cells ranges from 20 to 50 nm, and the gap between capillary lymphatic endothelial cells ranges from 120 to 500 nm, with an underdeveloped basement membrane. Therefore, carbon nanoparticles cannot enter the blood vessels when injected into the thyroid tissue; it rapidly enters the lymphatic vessels or lymphatic capillaries through phagocytosis by macrophages and is retained in the lymph nodes. In thyroid surgery, by injecting nano-charcoal into the thyroid gland, the nano-charcoal can diffuse through the gland and the lymphatic system, thus staining the thyroid tissue and lymph nodes black, while the tissues not subject to the lymphatic return of the thyroid gland will not be stained, such as parathyroid glands, the trachea and the supraglottic laryngeal reentrant nerve, which can keep their original color, different from the thyroid tissue and lymph nodes, thus playing an effective role in the protection. Protecting effect.

As a third-generation tracer, carbon nanoparticles suspension is highly conductive to the lymphatic system, especially in the display of small lymph nodes (<2mm), and the staining is fast-acting, long-lasting, effective in identifying parathyroid glands, and mildly toxic. The importance of charcoal carbon nanoparticles in parathyroid protection has been noted by many thyroid surgeons and many clinical trials have been conducted. It has been demonstrated that intraoperative injection of carbon nanoparticles can effectively increase the quality of intraoperative parathyroid gland detection and lymph node dissection, and reduce postoperative hypocalcemia and other adverse reactions, and at the same time, the carbon nanoparticles suspension injections in this trial have a high degree of safety, and no patients had allergic reactions to the injections.

However, there is no complete clinical guideline for preoperative intraglandular injection of carbon nanoparticles, and there is no standardized dosage for the appropriate injection time, injection dose, and injection method. Meanwhile, there is still the problem of carbon nanoparticles leakage during the procedure, which may affect the recognition and protection of the parathyroid glands by accidentally coloring the thyroid region black.

It is well known that the use of charcoal CNS is usually performed during surgery, but in our medical center, we found that preoperative injection of carbon nanoparticles by fine needle aspiration under ultrasound guidance can have better results by reducing CNS leakage in the surgical area. Possible reasons for this include:

- (i) preoperative ultrasound-guided intra-glandular lobe injection of carbon

nanoparticles does not have to open the surgical peritoneum of the thyroid gland, which reduces possible lymphatic vessel damage and makes lymphatic drainage more consistent with normal physiology; (ii) preoperative injection allows for a more adequate time for lymphatic dispersion of the carbon nanoparticles; and (iii) preoperative labeling of suspected metastatic lymph nodes by carbon nanoparticles injection further improves the tracing effect of the lymph nodes.

II.Purpose of the study

The purpose of this study was to investigate the effect of carbon nanoparticles injections at different preoperative and intraoperative times on surgical procedures and postoperative complications in patients with unilateral and bilateral papillary thyroid cancer or lymph node metastases.

III.Study population

One hundred and fifty patients who came to our hospital from January 2025 to June 2025, who were diagnosed with unilateral bilateral PTC or lateral LN metastasis by preoperative FNA (fine needle aspiration) or preoperative ultrasonography suggestive of TRAIDs grading 4a and above, and who were proposed to undergo laparoscopic thyroid surgery, were selected. Based on the objective conditions and subjective requirements of the patients, these patients were first divided into a partial thyroidectomy group (i.e., a unilateral lobectomy or partial thyroidectomy was performed) and a total thyroidectomy group (a total thyroidectomy was performed), and under the two groups, according to the timing of carbon nanoparticles injections, they were divided into two subgroups: a preoperative subgroup and a suboperative subgroup. In the preoperative subgroup, carbon nanoparticles was injected into the thyroid gland 2-6 hours prior to surgery, whereas in the suboperative subgroup, carbon nanoparticles was injected intraoperatively.

Inclusion Criteria:

- (1).Preoperative pathological assessment indicated the presence of thyroid cancer

with a maximum diameter of less than 4 cm.

(2). Postoperative pathological evaluation confirmed bilateral thyroid cancer or lateral lymph node metastasis.

(3). Vocal cord examination conducted one week prior to surgery revealed no abnormalities.

(4). The patient had no history of prior thyroid surgery and required a total thyroidectomy.

(5). Blood pressure was stably controlled.

(6). The patient regained consciousness and was able to communicate normally.

Exclusion criteria

(1) Prior to enrollment, the patient had received radiotherapy, chemotherapy, or isotope therapy;

(2) A documented history of thyroid surgery;

(3) Age under 16 years;

(4) Known allergies to the medications under investigation or an inability to tolerate surgical intervention;

(5) Presence of a retrosternal thyroid tumor;

(6) Tumor invasion of the parathyroid glands and/or the recurrent laryngeal nerve during surgical procedures;

(7) Postoperative pathology suggestive of medullary carcinoma or undifferentiated carcinoma;

(8) Development of a postoperative tracheal fistula.

IV. Observation indicators

(1). General information: age; gender; height; weight; BMI; tumor size; tumor location; pathology results; preoperative serum calcium; preoperative thyroid hormone;

(2). Preoperative parathyroid hormone levels; preoperative TSH; preoperative vocal cord movement problems.

(3). Carbon nanoparticles injections: carbon nanoparticles injection site; number of carbon nanoparticles injection needles; carbon nanoparticles injection dose.

(4). Carbon nanoparticles staining: thyroid staining; lymph node staining; parathyroid staining; nanocarbon leakage.

(5). Intraoperative data: length of surgery, number of lymph nodes cleared, amount of intraoperative bleeding.

(6). Postoperative data: postoperative pain duration; postoperative drainage; postoperative hospitalization; postoperative serum parathyroid hormone; postoperative laryngeal recurrent nerve stimulation and injury; postoperative hematoma; postoperative tracheal fistula.

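### Inclusion (2) is settled on postoperative pathology, after the injection being compared, so the timing subgroups can be selected differently through its lateral-node limb

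*Protocol*

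**What the plan says.** Section III of the protocol identifies patients from preoperative work-up, as those "who were diagnosed with unilateral bilateral PTC or lateral LN metastasis by preoperative FNA (fine needle aspiration) or preoperative ultrasonography" of a stated grade. They are split by extent of thyroidectomy and then by injection timing. On timing: "In the preoperative subgroup, carbon nanoparticles was injected into the thyroid gland 2-6 hours prior to surgery". The other subgroup receives its injection during the operation. No method of allocation to timing is given.

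The inclusion criteria in the same section then add, as item (2): "Postoperative pathological evaluation confirmed bilateral thyroid cancer or lateral lymph node metastasis".

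Background section I.3 lists possible reasons why preoperative injection may do better. Reason (ii) is that "preoperative injection allows for a more adequate time for lymphatic dispersion of the carbon nanoparticles". Reason (iii) is that "preoperative labeling of suspected metastatic lymph nodes by carbon nanoparticles injection further improves the tracing effect of the lymph nodes". The same section credits the tracer with showing nodes under 2 mm and, given intraoperatively, with better node dissection.

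Section IV lists lymph node staining and "number of lymph nodes cleared" among the observation indicators. It also lists postoperative tracheal fistula, which is exclusion (8).

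**The concern.** An eligibility rule should rest on facts fixed before the exposure. Inclusion (2) rests on a fact that arises after it, and one that the study hypothesis says the exposure may influence. A patient without bilateral cancer qualifies only if a positive lateral node is removed and confirmed. If preoperative injection traces such nodes better, more of these patients qualify in the preoperative subgroup, and the additional ones are those whose metastases are harder to find.

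Two kinds of result are exposed. Node counts and node staining are linked directly to the filter, because confirmation depends on which nodes were removed. Complication rates can shift if the additional patients carry a different risk from the rest, even when timing has no effect on complications. Nothing in the protocol says that injected patients who fail (2) stay in the comparison.

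**Working it through.** **Order of events.** Section III: preoperative FNA or ultrasound, then injection (2-6 hours before surgery, or during it), then surgery, then pathology. Inclusion (2) is read at the last step in both subgroups.

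**Which limb is affected.** Bilateral cancer is a finding in the gland, and nothing in the protocol suggests that injection timing changes it. Only the lateral-node limb can depend on timing.

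The protocol gives no detection rate, risk contrast or share of bilateral disease, so there is no stated figure to reproduce. All inputs below are assumptions unless a source is given.

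**Check 1: share eligible, with the bilateral limb included.** Let b be the share with bilateral cancer, L the share of the rest with a true lateral metastasis, and s the chance that it is found and confirmed.
- Eligible share: q = b + (1 - b) × L × s.
- Share of the eligible preoperative subgroup that would not have qualified under intraoperative injection: x = (1 - b) × L × (s_pre - s_intra) / q_pre.
- Number injected: 75 per subgroup (150 / 2, equal split assumed).
- Extreme contrast: give these additional patients a 7% risk and all others 38%, the two ends of the range for temporary hypoparathyroidism in section I.2. With no true effect, the preoperative rate is then lower by (0.38 - 0.07) × x = 0.31x.

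| b | L | s intra / pre | eligible of 75, intra / pre | x | spurious difference, points |
|---|---|---|---|---|---|
| 0.6 | 0.2 | 0.8 / 0.9 | 49.8 / 50.4 | 1.2% | 0.4 |
| 0.6 | 0.5 | 0.8 / 0.9 | 57.0 / 58.5 | 2.6% | 0.8 |
| 0.2 | 0.2 | 0.8 / 0.9 | 24.6 / 25.8 | 4.7% | 1.4 |
| 0.2 | 0.5 | 0.8 / 0.9 | 39.0 / 42.0 | 7.1% | 2.2 |
| 0.2 | 0.5 | 0.6 / 0.9 | 33.0 / 42.0 | 21.4% | 6.6 |
| any | any | equal | equal | 0 | 0 |
| 1.0 | any | any | 75 / 75 | 0 | 0 |

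Last numeric row in full: q_intra = 0.2 + 0.8 × 0.5 × 0.6 = 0.44; q_pre = 0.2 + 0.8 × 0.5 × 0.9 = 0.56; x = 0.12 / 0.56 = 0.214; 0.31 × 0.214 = 0.066. If the two risks are swapped, the sign reverses.

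**Check 2: case mix, without the bilateral limb.** Half the patients have bulky nodes (always confirmed, 20% complications). Half have small metastases (8% complications), confirmed with probability d. The observed rate is (0.5 × 0.20 + 0.5 × d × 0.08) / (0.5 + 0.5 × d).
- d = 0.6 vs 0.7 (intraoperative vs preoperative): 0.124 / 0.80 = 15.5% vs 0.128 / 0.85 = 15.1%.
- d = 0.5 vs 0.8: 0.120 / 0.75 = 16.0% vs 0.132 / 0.90 = 14.7%.
- d = 0.3 vs 0.9: 0.112 / 0.65 = 17.2% vs 0.136 / 0.95 = 14.3%.

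The spurious difference is about 0.4 to 2.9 points.

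**Check 3: nodes cleared.** Gamma-Poisson node counts with mean 8 in both subgroups and shape k; per-node chance of being positive p = 0.10 intraoperative, 0.20 preoperative. P(no positive) = (1 + 8p/k)^(-k). Mean nodes among those qualifying = [8 - 8(1 - p)(1 + 8p/k)^(-(k+1))] / [1 - P(no positive)].
- k = 4: (8 - 2.894) / 0.518 = 9.9 vs (8 - 1.190) / 0.740 = 9.2; 52% vs 74% qualify.
- k = 2: (8 - 2.624) / 0.490 = 11.0 vs (8 - 1.097) / 0.691 = 10.0; 49% vs 69% qualify.

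True means are equal, yet the filter makes the intraoperative subgroup look higher. Adding a bilateral limb shrinks this. With b = 0.4 and k = 4: (0.4 × 8 + 0.6 × 5.106) / (0.4 + 0.6 × 0.518) = 8.8 vs (0.4 × 8 + 0.6 × 6.810) / (0.4 + 0.6 × 0.740) = 8.6.

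**The case against.** The strongest reply is that lateral dissection is largely decided before any tracer is given. Section I.1 reserves zone II-VI dissection for patients whose nodes are positive or highly suspected on work-up, and reason (iii) in section I.3 concerns nodes already suspected. On that reading, timing hardly changes whether the lateral neck is opened. It may change yield within a dissection, which is a weaker mechanism than a node being missed altogether. The reasons are also offered as possibilities, not as established effects.

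This stands as a limit on size. It does not remove the problem, because the protocol still expects timing to affect node tracing and still reads eligibility afterwards.

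The illustrations are also open to attack. Check 2 and the main form of check 3 leave out bilateral disease, so they lean towards the worst case. The 20% vs 8% contrast has no support in the protocol, which attributes hypoparathyroidism to damaged blood supply or inadvertent removal of the glands. Check 3 lets any positive node meet a lateral criterion, although section I.1 makes central dissection the minimum. All of this stands, and it is why no single size or direction is claimed.

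A last reply is that no allocation method is stated, so comparability was never assured. True, but this selection would come on top of any confounding, and it can be removed by wording alone.

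**Conclusion.** The point holds in a limited form. Inclusion (2) selects after exposure, and the protocol's rationale makes part of it a possible consequence of exposure. For patients without bilateral cancer, the two timing subgroups can therefore be selected differently.

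A reader might infer more: that the subgroups are in fact selected differently and have lost comparability, that every patient with failed tracing disappears, or that the preoperative complication rate must look too low. The documents support none of these. Comparability was not established beforehand. Bilateral patients stay whatever the tracing, as do patients whose positive node is removed unstained. The direction for complications depends wholly on an assumed risk contrast, and the node illustration runs against preoperative injection.

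The bias is zero with equal detection or all-bilateral disease. The upper figure of 6.6 points needs a low bilateral share, a large detection gap and the extreme 7% vs 38% contrast together. The fault itself rests on none of these inputs. It is a stated eligibility rule, not a detail left to an analysis plan.

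**What to change.** 1. Define criterion (2) on the preoperative FNA or ultrasound findings that section III already uses, fixed before injection. Reconcile its disease scope with sections II and III, which also name unilateral disease; criterion (2) as written covers only bilateral cancer or lateral node metastasis.
2. Do not remove injected patients from the main comparison because pathology fails to confirm bilateral or lateral nodal disease.
3. Report pathological confirmation of lateral metastasis by timing subgroup, and show the pathology-confirmed set as a secondary analysis.
4. Review exclusions (6), (7) and (8) in the same way. Exclusion (7) turns on tumour type, which timing is unlikely to change; if (6) or (7) is kept, report the number removed in each timing subgroup. Exclusion (8), tracheal fistula, is itself a listed outcome, so patients who develop it should stay in the analysis.

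With step 1, the difference in eligibility under (2) caused by timing is zero by construction. Confounding from the unstated allocation remains. The cost is rewording criterion (2), a decision on three exclusions, and a somewhat more mixed population, because some patients with unconfirmed disease stay in. The protocol is dated 11 January 2025 and recruitment was to run from January to June 2025, so the wording could have been corrected early in recruitment.

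### Inclusion criterion (4) admits only patients who need a total thyroidectomy, yet section III defines a partial-thyroidectomy group; criterion (2) also excludes part of the stated target population

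*Protocol*

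**What the plan says.** **Groups (Protocol, section III, opening paragraph).** Entry is open to patients "who were proposed to undergo laparoscopic thyroid surgery", with no limit on the extent of surgery. The division by surgery is made "Based on the objective conditions and subjective requirements of the patients". The first group is introduced as follows: "these patients were first divided into a partial thyroidectomy group (i.e., a unilateral lobectomy or partial thyroidectomy was performed". The same sentence then names the second group, defined by the larger operation: "and a total thyroidectomy group (a total thyroidectomy was performed". The timing split is placed beneath both: "under the two groups, according to the timing of carbon nanoparticles injections, they were divided into two subgroups". The timing comparison is therefore planned inside both surgery groups.

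**Eligibility (section III, Inclusion Criteria).** There is one list for the whole study. Item (4) reads: "The patient had no history of prior thyroid surgery and required a total thyroidectomy". Item (2) requires postoperative pathology to show cancer on both sides or spread to lateral nodes. Neither item is tied to a surgery group.

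**Target population.** Section II describes the study as being "in patients with unilateral and bilateral papillary thyroid cancer or lymph node metastases". Section III describes patients "who were diagnosed with unilateral bilateral PTC or lateral LN metastasis by preoperative FNA".

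**The concern.** The group definition and the eligibility list describe different populations. Section III needs patients who have a lobectomy or other partial operation, and item (4) accepts only patients who need the whole gland removed. Whoever screens patients has to break one of the two passages.

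If the list is followed, the partial group loses the patients it was set up for and the study cannot compare injection timing in them. If section III is followed, every intended partial-surgery patient enters against a written criterion, and an analysis restricted to eligible patients would have to drop them. A statistical analysis plan cannot settle this, because it cannot make an ineligible patient eligible.

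Item (2) adds a related problem. The Purpose promises an answer for unilateral papillary cancer and attaches no nodal condition to it, but item (2) lets unilateral disease in only when lateral nodes are positive. Correcting (4) alone would leave that gap.

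**Working it through.** The check is one of text and logic. There is no plan figure to reproduce: 150 is stated as a total, without a split by surgery group, timing or disease extent.

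**Step 1: cells of the design.** Section III gives 2 surgery groups × 2 injection timings = 4 cells. Item (4) is applied to each.

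| Surgery group | Timing | Intended patients meet inclusion (4)? |
|---|---|---|
| Partial | Preoperative | No |
| Partial | Intraoperative | No |
| Total | Preoperative | Yes |
| Total | Intraoperative | Yes |

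Result: the intended patients of 2 of 4 cells are barred.

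**Step 2: is item (4) only about previous surgery?** Exclusion (2) already removes patients with earlier thyroid surgery. What item (4) adds is the extent of the operation, so that half of the sentence cannot be read away.

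**Step 3: disease extent.** Laterality (unilateral, bilateral) × lateral node metastasis (yes, no) = 4 combinations. Inclusion (2) is an either/or condition.

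| Laterality | Lateral nodes | Meets inclusion (2)? | Within the Purpose? |
|---|---|---|---|
| Bilateral | Yes | Yes | Yes |
| Bilateral | No | Yes | Yes |
| Unilateral | Yes | Yes | Yes |
| Unilateral | No | **No** | **Yes** |

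Result: 3 of 4 combinations are admitted and 1 is barred. Because unilateral disease with lateral nodes passes, item (2) does not by itself empty the partial group.

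**Step 4: correct (4) only.** Item (4) would then bar 0 of 4 cells, but the same 1 of 4 disease combinations would stay barred in both surgery groups.

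These are counts of cells and categories, not of patients.

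**The case against.** **Needing versus receiving.** Item (4) speaks of the operation a patient needed, while section III forms the groups by the operation done and partly by patient preference. A patient judged to need total thyroidectomy who chose less could satisfy both passages, so the partial cells need not be strictly empty. This much stands, and it is why the claim concerns the intended patients of those cells. It does not rescue the text. The protocol never states this reading, and the split also rests on objective conditions, which would have no evident part in assigning partial surgery if everyone needed the total operation. The partial group would then consist only of people who had less surgery than they were judged to need, a population the Purpose does not describe.

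**The partial group may be the slip.** It has its own definition in parentheses, and the timing split is placed expressly under both groups. The Background remarks on extent of resection are general and prove nothing about this study's groups, so no weight is put on them. Which passage is wrong is in any case left open here.

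**Unilateral disease.** Section III's phrase lacks a conjunction and is weak evidence taken alone. That is fair, but the Purpose is clear and carries the point without it.

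**Scope.** The comparison within total thyroidectomy is unaffected by item (4). This stands: the main defect concerns one of the two surgery groups. The count of 1 in 4 disease combinations also says nothing about how common the barred combination is.

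**Conclusion.** The concern holds. As written, inclusion (4) contradicts the group structure in section III and bars the intended patients of 2 of the 4 cells. Inclusion (2) separately bars unilateral papillary cancer without lateral nodes, which the Purpose includes.

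The conclusion rests on two readings: that the one inclusion list applies to all patients, since nothing limits it, and that the partial group is meant for patients in whom partial surgery is planned. The number of patients affected cannot be given without a split of the 150. The contradiction must be resolved because it decides who may be enrolled and whether one of the two planned timing comparisons exists at all.

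**What to change.** Make the Purpose, section III and inclusion (2) and (4) describe one population. There are two ways:

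1. **Keep both surgery groups.** State items (2) and (4) separately for each group, so that the patients whom section III groups are eligible and the unilateral disease named in the Purpose is covered.
2. **Keep the inclusion list.** Remove the partial group and bring the unilateral wording in the Purpose and section III into line with item (2), then limit the conclusions to match.

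The documents do not show which was meant, and the choice belongs to the sponsor and investigator. No surgical rule is proposed here.

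**Cost.** The first option changes protocol wording only. The second is larger: it removes a design stratum, and the 150, stated for both groups together, would have to be restated. In either case, item (2) depends on postoperative pathology, which is known only after injection and surgery. While it is being reworded, the protocol should say how it is applied to patients already treated. The document is dated 2025.01.11 and recruitment runs from January to June 2025, so any patients already entered need to be checked against the reconciled text. The earlier this is done, the fewer there will be.

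### Inclusion (6) has no time point and is worded as a post-anaesthesia condition; if applied after surgery, it could exclude patients with the severe complications the study is meant to compare

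*Protocol*

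**What the plan says.** Inclusion (6) in Protocol section III is one sentence: "The patient regained consciousness and was able to communicate normally". It does not say when this is judged, by whom, or what counts as normal communication.

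The stated purpose in section II is the effect of injection timing "on surgical procedures and postoperative complications in patients with unilateral and bilateral papillary thyroid cancer or lymph node metastases". Section IV (6) lists among the postoperative data "postoperative laryngeal recurrent nerve stimulation and injury; postoperative hematoma; postoperative tracheal fistula".

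Section I.2 (2) describes what nerve injury does. For one side: "Patients with unilateral recurrent laryngeal nerve injury will suffer from hoarseness", together with mild breathing and swallowing difficulty. For both sides: "patients with bilateral recurrent laryngeal nerve injury will suffer from respiratory difficulties, respiratory failure, and even asphyxia in severe cases".

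The eligibility list mixes time points. Inclusion (2) is dated after surgery: "Postoperative pathological evaluation confirmed bilateral thyroid cancer or lateral lymph node metastasis". Inclusion (3) is dated before it: "Vocal cord examination conducted one week prior to surgery revealed no abnormalities". Inclusion (5), on blood pressure, is undated like (6). Exclusions (6) to (8) rest on findings during or after surgery.

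**The concern.** Eligibility should be settled on facts that exist before the injection. A criterion met only on waking from surgery comes after both the injection and the operation, so the complications being compared can affect it. A patient in respiratory failure from bilateral nerve injury would plausibly fail a test of normal communication. That patient would then leave the study as ineligible and would not be counted as an event.

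At stake is the complication comparison, one of the stated purposes. The most severe cases would be the first to go. Patients dropped as ineligible may also have no outcome recorded, so the analysis might not be able to restore them.

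**Working it through.** The protocol has no figure of its own to reproduce here: it states 150 patients and no nerve-injury rate. The check is therefore a reading of the text, followed by an illustration on assumed rates.

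**Step 1: what time does (6) refer to?**

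- For a postoperative reading: the verb means recovering something lost. All patients are scheduled for laparoscopic thyroid surgery (section III), and the protocol describes no other loss of consciousness. The same list uses later facts in inclusion (2) and exclusions (6) to (8).
- For a baseline reading: (6) names neither surgery nor anaesthesia, carries no postoperative label, and follows (3) to (5), which are preoperative or baseline in kind.

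The text does not settle the question. The literal wording favours the first reading, and the position in the list favours the second.

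**Step 2: if postoperative, does it touch the outcomes?** Section I.2 (2) links bilateral injury to respiratory failure and asphyxia, which can prevent normal communication. Section IV (6) lists nerve injury and hematoma as observations. Inclusion could then depend on an outcome. For unilateral injury the answer turns on whether a hoarse patient communicates normally, which is not defined.

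**Step 3: how many patients?** Assumed shares of the 150 who fail (6) because of a postoperative event:

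- 0.5%: 150 × 0.005 = 0.75 patients
- 2%: 150 × 0.02 = 3 patients
- 5%: 150 × 0.05 = 7.5 patients

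**Step 4: what happens to the comparison?** Let *r* be the true rate of nerve injury and *s* the share of injured patients removed, equal in both timing subgroups. Removed patients leave numerator and denominator, so

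observed rate = r(1 − s) / (1 − rs).

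Assumed, not from the protocol: r = 8% and 4%. The event column further assumes 75 patients per timing before removal, so the full count is 75 × 0.08 + 75 × 0.04 = 9, and 9(1 − s) remain.

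| s | Higher rate | Lower rate | Difference (points) | Ratio | Events left |
|---|---|---|---|---|---|
| 0 | 8.0% | 4.0% | 4.0 | 2.00 | 9 |
| 0.25 | 0.06/0.98 = 6.1% | 0.03/0.99 = 3.0% | 3.1 | 2.02 | 6.75 |
| 0.50 | 0.04/0.96 = 4.2% | 0.02/0.98 = 2.0% | 2.1 | 2.04 | 4.5 |
| 0.90 | 0.008/0.928 = 0.9% | 0.004/0.964 = 0.4% | 0.4 | 2.08 | 0.9 |

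The row s = 0.90 is an extreme: it needs nearly every injured patient, including those who are only hoarse, to be dropped. With equal removal the ratio stays at about 2, while the absolute difference and the number of events shrink.

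If removal were unequal, the ratio could move either way. With 50% removed from the higher-rate subgroup and 25% from the other it is 4.17/3.03 = 1.4; with the shares reversed it is 6.12/2.04 = 3.0.

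**The case against.** A reader might infer that (6) is a postoperative filter that does remove severe nerve and airway complications. The protocol does not support that as a fact. The criterion is undated. Where this list means a late time point it usually says so, and here it does not. The English is loose throughout, and the past tense is also used for plainly baseline conditions such as blood pressure. A clumsy way of requiring a conscious, communicative patient at enrolment is a plausible reading, and on that reading no complication is lost.

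Even on the postoperative reading the loss is conditional. Hoarseness need not prevent normal communication, and a patient may recover before an assessment whose time is not given. Nothing says that patients with nerve injury or hematoma are excluded, and section IV (6) plans to record both.

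A reader might also infer that the criterion could hide a relative effect of timing. With equal removal it would not: the ratio barely moves, and the loss is in absolute difference and precision. The rates and removal shares used above are assumptions.

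These objections limit the claim but do not remove it. A site that followed the literal wording would not be misreading it. Elsewhere this protocol does select on an outcome in plain terms: exclusion (8) removes postoperative tracheal fistula, which section IV (6) lists. That is a separate and clearer case, but it shows that the postoperative reading of (6) is not far-fetched.

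**Conclusion.** The point holds in conditional form. Inclusion (6) has no time point and is worded as a post-anaesthesia condition. If applied after surgery, it could exclude patients with severe nerve injury or airway compromise and so lower the observed complication rates, the absolute difference and the number of events.

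The protocol does not allow the size to be derived. Under the assumed failure shares of 0.5% to 2%, about 1 to 3 of 150 patients would be lost. That is small in number, but severe complications are likely to be few when 150 patients are spread over two surgical groups and two timings. The statement that the ratio changes little rests on equal removal in both subgroups.

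Because a badly worded baseline criterion is a plausible alternative, this is not a critical flaw. It is still more than a missing detail, because following the sentence as written can make inclusion depend on an outcome.

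**What to change.** Reword (6) as a baseline condition judged before injection: the patient is conscious and able to communicate normally at preoperative assessment. Add that no patient is removed for the state in which they wake from surgery, and that patients who cannot communicate afterwards stay in the study and are counted under the nerve-injury, hematoma or other complication items of section IV (6).

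This is sound under either reading. If baseline was intended, it only states the intention; if not, it closes the route to selection on outcome. The cost is a sentence or two in the eligibility criteria, and complication rates may be reported slightly higher.
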